2.0	1 Nov 2022	
 ● Added section about variations from original evaluation ● Updated number of FDAC sites and Local Authorities included in the study (Table 1) ● Updated Identification strategy section: changed severity of alcohol and drug misusing into type of misuse due to non-FDAC data availability ● Updated Outcome measure section: added an additional analysis of the number of different types of expert witness to deal with Research Question 5 ● Updated Matching section: updated Table 3 on matching variables; coarsening strategy for child, parent and case-level outcomes; and variables to be used by children-, parent- and case-level (details on changes can be tracked by comparing previous version of Table 3 “Intended variables for matching” in Appendix C) ● Updated Analysis plan section: changed model specification into a multilevel logistic regression to account for clustering effects; added a multilevel Poisson regression model to explore the difference between FDAC and non-FDAC cases in the number of different types of expert witness consulted during care proceedings. ● Updated Data source and availability section, in accordance with non-FDAC data availability ● Added new table listing misalignment between FDAC and non-FDAC data, along with derived variables to harmonise the data (Table 5) ● Updated Ethics & Participation section: regarding local authorities having to send out opt-out letters to parents receiving non-FDAC care proceeding ● Updated personnel list and timeline ● Expanded the date window for eligibility for study inclusion to maximise our sample size 
Minor changes:
 
 ● Used consistent terminology for child-, parent-, and case-levels of data ● Refer to the comparison group as non-FDAC care proceedings as usual, to match the language used with LAs ● Simplified the power analysis table to remove clusters with ICC = 0. (No change to calculation)

Table of contents

Table of contents	3
Background and Problem Statement	4
Children and Families Act 2014	4
The National Unit	4
Effectiveness	4
Variation between sites	5
Rationale for further evaluation of FDAC	5
Variations from original evaluation design	5
Intervention and Theory of Change	6
Impact Evaluation	8
Research questions	8
Participants	8
Design	9
Identification strategy	10
Data sources and availability	11
Minimum detectable effect size calculations	17
Outcome measures	18
Analysis plan	19

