Primary carer for how many children	N/A	Number of children in household	We will derive a new parent-level variable from child-level data, counting how many children each parent cares for as primary carer, for both FDAC and non-FDAC groups.
Primary carer – Age of youngest child cared for	N/A	Age of youngest child in household	We will derive a new parent-level variable from child-level data, selecting the age of the youngest child the parent cares for as primary carer.
Number of children in the case	N/A	Number of children in household	We will derive a new case-level variable that is a count of the number of children in the case.
Age of youngest child in the case	N/A	Age of youngest child in household	We will derive a new case-level variable, calculated from the age variable in the child-level data.
Substance misuse type	Severity of parental alcohol misuse: High, Medium, Low, None, Unknown*	Substance misuse type: Drugs, Alcohol, Drugs and Alcohol, None, Unknown	FDAC data will be recoded to match non-FDAC data as follows: 1) If misusing at time of referral = No, we will code the substance misuse type as None; 2) If misusing at time of referral = Yes, we will check parental alcohol misuse and drug misuse and categorise their substance misuse type as Drugs, Alcohol, Drugs and Alcohol, or Unknown; 3) If misusing at time of referral = Unknown, we will recode the substance misuse type as Unknown
	Severity of parental drug misuse: High, Medium, Low, None, Unknown*		

*This is based on clinical judgements on substance misuse severity where guidance for the FDAC data collection tool is provided in Appendix D.

Minimum detectable effect size calculations

Power calculations were conducted in Stata 17.1 based on the anticipated matched sample size, using formulae from Dong and Maynard (2013). These formulae are presented in Appendix F. The results are presented in Table 5. The total number of non-FDAC cases will exceed the numbers prior to matching. Cases are then weighted so that there are equivalent FDAC and non-FDAC cases, so we assume equal sample sizes at analysis. Our assumptions are:

- Clustering of children within parents, with an ICC of 0.70
- No clustering of children within Local Authorities
- Variance explained by the uncoarsened covariates used in a regression model after matching, with an R-squared of 0.20 at level one and 0.10 at level two. We estimate this to provide a correlation of 0.45 and 0.32 respectively⁷

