- That 25% of children in control are reunified with their parents by the end of care-proceedings (informed by Harwin et al., 2018)
- A type one error rate of 0.05
- Power of 0.80 (a type two error rate of 0.20)
- Two tailed significance testing

There is some uncertainty on the expected sample size. Based on Harwin et al. (2018) we anticipate that each FDAC case will have a mean of 1.4 children. Our assumptions use this figure and build on estimates of expected caseloads for the implementation period (January 2021 – June 2022) collected by FDAC sites by CJI in Summer 2020. Based on updated figures concerning expected caseloads, we anticipate a sample of 300 intervention children from 215 cases.

Based on these assumptions, we expect the evaluation will be powered to detect a relative risk ratio of 1.36 (or equivalent to a 9.1 percentage point difference). No power calculations are conducted for secondary analyses, but these will have lower power as the units of analyses are at the parent and case-levels. However, as the intracluster correlation coefficient is relatively large for child-level analyses, the reduction in power will be relatively small.

Table 5 Minimum detectable effect size calculation		
Relative Risk Ratio		1.36
Baseline/Endline correlations	Child	0.45
	Parent	0.32
Intracluster correlations (ICCs)	Parent	0.70
		0.00

⁷ Our sample size calculations include estimates of the proportion of variance explained through the included covariates at each of these levels (R^2). We have converted these into pre- post-test correlations by taking the square root of the R^2 value.

Social Worker Team		0.00
Alpha		0.05
Power		0.80
One-sided or two-sided?		2
Level of intervention clustering		Parent
Average cluster size (parent)		1.40
Sample Size (children)*	Intervention	300
	Control	300
	Total	600
Sample Size (cases)	Intervention	215
	Control	215
	Total	430

* Of which, we assume half are intervention children and half are matched control children

Outcome measures

The primary and secondary outcomes will be sourced from the FDAC data collection tool for intervention cases and Local Authority administrative data for control cases. Local Authorities will already collect data on reunification but may not systematically capture parental alcohol or substance misuse, contested final hearing and use of expert witnesses. This will be included in the data collection template prepared by NatGen.

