Appendix F – Power calculation formulae

The formula used to estimate the power of the primary analysis are adapted from Dong and Maynard (2013). The MDES is calculated as follows:

$$MDES = M_{K(J-2)-g_2} \sqrt{\frac{\rho(1-R_1^2)}{P(1-P)JK} + \frac{(1-\rho)(1-R_2^2)}{P(1-P)JKn}}$$

Where:

- ρ is the intracluster correlation;
- R_1^2 and R_2^2 is the variance explained at level one and level two respectively;
- n is the average number of children per family
- J is the average number of parents per Local Authority
- K is the number of Local Authorities

The multiplier, $M_{K(J-2)-g_2}$ is calculated as follows:

$$M_{K(J-2)-g_2} = T_1 + T_2$$

Where T_1 (precision) and T_2 (power) are drawn from the inverse students' t-distribution as:

$$T_1 = \alpha, K(J - 2) - g_2$$

$$T_2 = 2\beta, K(J - 2) - g_2$$

Where g_2 is the number of covariates at level two, alpha is the type one error rate and beta is the type two error rate. We then convert the MDES to an odds ratio:

$$OR = (MDES * \frac{\pi}{\sqrt{3}})^e$$

The relative risk ratio is then estimate using the prevalence of the outcome in control, $Prev_c$:

$$RRR = \frac{OR}{(1 - Prev_c) + (Prev_c * OR)}$$

Trial Evaluation Protocol
Family Drug and Alcohol Courts
Evaluator: NatCen Social Research
Principal investigator: [name]

Evaluation of Family Drug and Alcohol Courts

Intervention Developer	Family Drug and Alcohol Courts in England
Delivery Organisations	Family Drug and Alcohol Courts in England
Evaluator	NatCen Social Research
Principal Investigator	[name]
Protocol Author(s)	[name], [name], [name], [name]
Type of Trial	Quasi-experimental design: Coarsened Exact Matching
Age or Status of Participants	Parents in care proceedings; Children of Parents in care proceedings
Number of Participating Local Authorities	31
Number of Children and Families	600 children (300 intervention; 300 control): 430 families (215 intervention; 215 control)
Primary Outcome(s)	Reunification
Secondary Outcome(s)	Parental alcohol and drug misuse cessation, number of contested hearings, use of expert witnesses, parent-child relationship, parental mental health.
Contextual Factors	Covid-19

Table of contents

Table of contents	2
Background and Problem Statement	3
Intervention and Theory of Change	4
Impact Evaluation	6
Implementation and process evaluation	20
Cost evaluation	23
Ethics & Participation	24
Registration	24
Personnel	25
Timeline	25
References	27

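### The claimed 80% power for a relative risk of 1.36 rests on a continuous-outcome conversion; for the binary reunification outcome, the plan's own inputs at 300 per arm give about 64%

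*Supplement*

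**What the plan says.** In version 2.0, the section on minimum detectable effect size and Table 5 set out these inputs:

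- "A type one error rate of 0.05", with "Two tailed significance testing" and "Power of 0.80 (a type two error rate of 0.20").
- 25% of control children reunified.
- Average cluster size 1.4 and parent-level ICC 0.70, with no clustering by Local Authority.
- Covariate R-squared of 0.20 at child level and 0.10 at parent level.
- On numbers, "we anticipate a sample of 300 intervention children from 215 cases", with the same number of controls: "Cases are then weighted so that there are equivalent FDAC and non-FDAC cases, so we assume equal sample sizes at analysis".

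The result is given as "we expect the evaluation will be powered to detect a relative risk ratio of 1.36 (or equivalent to a 9.1 percentage point difference").

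Appendix F gives the route: a minimum detectable effect size in standard-deviation units from a clustered design formula, then "We then convert the MDES to an odds ratio" by way of π/√3, then a relative risk at the control prevalence. The Outcome measures section defines reunification as a binary indicator, and the Analysis plan fits a multilevel logistic model to it.

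**The concern.** Multiplying a standardised difference by π/√3 puts it on the log-odds scale of an underlying logistic variable. The standard error behind that difference is then the one that would apply if each child's underlying score were observed. The study observes only whether the child was reunified. A yes/no outcome at a rate near 30% carries less information than the score, so the same number of children gives less power.

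The plan justifies the study partly by larger samples that can detect smaller effects, and this section is its only statement of what the study can detect. If the true effect were 9.1 points, the chance of missing it would be about 36% rather than 20%. A null result could then be taken as stronger evidence against an effect of that size than it is.

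**Working it through.** **1. Reproduce the plan's figure.** With P = 0.5, 430 cases and 600 children, and with the parent-level R-squared on the between-parent term and the child-level R-squared on the within-parent term:

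- Variance = 0.70 × (1 − 0.10) / (0.25 × 430) + 0.30 × (1 − 0.20) / (0.25 × 600) = 0.00586 + 0.00160 = 0.00746.
- MDES = 2.80 × √0.00746 = 0.242.
- OR = exp(0.242 × π/√3) = 1.55.
- RR = 1.55 / (0.75 + 0.25 × 1.55) = 1.36, which is 9.1 points.

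Using t rather than normal quantiles gives 1.364. So 1.36 follows from the stated route.

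**2. See what the route assumes.** It gives each child a log-odds variance of π²/3 = 3.29. For a binary outcome the figure is 1/[p(1 − p)]. At the mean rate (0.25 + 0.341)/2 = 0.2955 this is 1/0.208 = 4.80. The implied standard error is therefore √(3.29/4.80) = 0.83 of what it should be, or about 17% too small.

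**3. Recompute with binomial variance.** The same variance term corresponds to 2/0.00746 = 268 independent children per arm. For 25% versus 34.1%:

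- Null standard error = √(2 × 0.2082 / 268.1) = 0.0394.
- Alternative standard error = √[(0.1875 + 0.2247) / 268.1] = 0.0392.
- Power = Φ[(0.091 − 1.96 × 0.0394) / 0.0392] = Φ(0.35) = 63.7%.

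The test statistic hardly matters: 64.1% unpooled, 63.4% on the log odds ratio, 63.9% arcsine.

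**4. Detectable effect.** With 268 per arm, 80% power is reached at 36.1%: 11.1 points, RR 1.44 to 1.45. Detecting 34.1% with 80% power needs 394 effective children per arm, which on the plan's inputs is 300 × 394/268 ≈ 441 children (316 cases) per arm.

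**5. Vary what the plan leaves open.**

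| Reading, at 300 children per arm | Power for 25% v 34.1% |
|---|---|
| Plan's inputs, observed scale | 64% |
| ICC of 0.70 taken as latent-scale | 68% |
| ICC 0.50, plan's R-squared | 67% |
| R-squared placed as printed in Appendix F | 66% |
| No gain from covariates | 58% |
| Simulated clustered binary data, robust logistic regression | 54–61% |

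A check that needs neither the ICC nor R-squared: 300 fully independent children per arm, with no covariates, give 69%.

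**6. Vary the effective sample.** These sizes are assumptions; the plan does not give them.

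| Effective sample | Result |
|---|---|
| 50% of 268 per arm | 80% power at RR 1.64 |
| 80% of 268 per arm | 80% power at RR 1.50 |
| 268 per arm | 80% power at RR 1.44–1.45 |
| 2:1 matched controls, before weighting loss | 77% power for RR 1.36 |
| 2.5:1 matched controls, before weighting loss | about 80% power for RR 1.36 |
| Both arms 1.47 times larger | 80% power for RR 1.36 |

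**The case against.** The plan discloses its method in full, and 1.36 reproduces from it. This is therefore an unsuitable method, not a slip in arithmetic. That is right, but it does not rescue the 80%.

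A stronger objection is that 64% holds only for a strict 300/300. Eligibility now starts in October 2019, while the caseload estimates cover January 2021 to June 2022. The Identification strategy aims for more controls than FDAC cases, and its weights keep every matched control. Both could raise power, as the last three rows of step 6 show. This stands as a reason to show sensitivity in both directions. The plan promises no such sizes, though, and its own calculation is for 300 per arm.

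It can also be said that no test or decision rule uses the figure, and that reporting relative risks with confidence intervals will show what a null result excludes. That limits the damage without making the statement correct.

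Four stronger readings are tempting but unsupported:

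- **That the fall from 31 to 12 Local Authorities invalidates the figure.** Clustering by Local Authority is set to zero, so their number enters only through the degrees of freedom; RR is 1.364 either way. The version history's "No change to calculation" is therefore no fault on this ground.
- **That the matched sample shrinks to 9/14 because only nine of the 14 FDAC sites have a control Local Authority.** Neither site nor Local Authority is a matching variable in Table 3, so a child from a site without local controls can be matched elsewhere.
- **That the printed formulae produced a wrong result.** Appendix F as shown puts the R-squared terms on the opposite levels (RR 1.35 if used so) and raises to the power e (odds ratio 0.11 if taken literally). The stated 1.36 requires the proper placement and exp(), so neither affected it. They may even be faults of text extraction.
- **That the plan takes every anticipated FDAC child to be matched.** It calls its numbers the anticipated matched sample while deriving them from caseloads, so this is unclear rather than shown.

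**Conclusion.** The statement of 80% power for a relative risk of 1.36 is wrong for a binary outcome on the plan's own inputs. At 300 children and 215 cases per arm, power for 25% versus 34.1% is about 64%, and the effect detectable with 80% power is about 11.1 points (RR 1.44 to 1.45).

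The 64% takes the ICC of 0.70 and the R-squared values as applying on the observed binary scale, and it counts no loss from CEM weighting and no clustering by site. Other readings of the ICC and R-squared give roughly 54% to 68%, so the exact value is uncertain, but none at 300 per arm reaches 80%. It is not a forecast of the power the study will have, because the matched numbers may turn out larger or smaller.

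**What to change.** - Replace the power statement and Table 5 with a binary-outcome calculation: at a fully matched 300/300, 80% power for RR about 1.44 to 1.45 (25% versus about 36.1%, 11.1 points).
- State whether the ICC and R-squared are on the observed or the latent scale.
- Add rows for other matched or effective sizes after CEM weighting, in both directions and labelled as assumptions. Examples are RR 1.50 at 80% and 1.64 at 50% of the effective size, and about 77% power for RR 1.36 with 2:1 matched controls before weighting loss.
- In Appendix F, check and correct the placement of the R-squared terms and print the odds-ratio step as an exponential. Both are presentational.

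The cost is a few recalculated lines and a less favourable headline figure. Sample, data collection and analysis do not change.

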The matching will be conducted using the user-written package *cem* in Stata 17.1 SE (Blackwell et al., 2010), which implements CEM as described in Iacus et al. (2009). The primary analysis will be conducted on an intention-to-treat basis where the outcome is non-missing. Where covariate data is missing, the *cem* package matches cases that are missing data on the same covariates. If missing outcome data exceeds five percent of the intervention sample, we will consider conducting a sensitivity analysis using multiple imputation (see missing data analysis).

Any intervention cases excluded from the analysis because no match can be found will be transparently reported using a CONSORT flow diagram. If more than five percent of intervention cases are lost because of issues with common support, we will consider adjusting how covariates are coarsened. This would involve collapsing categories of coarsened covariates and altering bin sizes. A summary of matching variables and how they will be coarsened can be found in Table 3.

Analysis

A “doubly robust” estimation of causal effects will be estimated for the matched sample, applying the weights assigned during the matching, including a binary indicator of allocation to FDAC, while also including the uncoarsened matching covariates in the regression model, following Funk et al. (2011). The “doubly robust” estimation reduces the risk that the average treatment effect on the treated (ATT) is biased, provided that either the matching (modelling exposure to the intervention) or the regression model (describing the relationship between the dependent and independent variables) is well specified (Funk et al., 2011). To account for the clustering of children within primary carers, cases and within sites (as shown in Table 1)⁸, we will use a multilevel logistic regression model. The full model is as follows:

$$P(\text{Reunification}_{ipcs}) = \text{logit}^{-1}(\beta_0 + \beta_1 \text{Intervention}_{ipcs} + \beta_2 X_{ipcs} + u_{pcs} + u_{cs} + u_s)$$

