We will calculate RRR as follows. First, we will calculate the conditional probabilities from the fitted coefficients of the multilevel logistic regression models by holding the covariates constant at their means.¹⁰ Second, we will then calculate relative risk ratios using the *nlcom* command in Stata, which returns the standard errors and confidence intervals of each ratio.

Exploratory Analysis

Additional analysis will be conducted to assess whether reunification can be sustained over time, as prior evidence (Harwin et al., 2019; Broadhurst et al., 2017) indicated that the greatest risk of returning to court for care proceedings are the first two years after reunification.

A prior cohort (2017 and 2018) of FDAC participants will be identified by FDAC sites. They will then share identifiers with Children Family Court Advisory and Support Service (Cafcass). Cafcass will then identify if children were returned to court for care proceedings in the subsequent three years. The analysis does not compare to a counterfactual as it will be drawing on historic data, and we do not expect comparable data for a control group to be available. This means a counterfactual cannot be constructed with matching. As this analysis will not use a counterfactual, it will not provide a causal claim, but we will compare to a national average.

¹⁰ Non-ordered categorical covariates will be represented as binary variables for each level.

We will also assess whether people who experience racism have different outcomes than those who do not. If the available data allows, we will also separate estimates for white FDAC participants and all other FDAC participants. We understand that different ethnicities may experience different impacts, and that white/non-white may mask underlying differences between different groups. However, we do not anticipate that the available sample sizes would support robust estimates for separate minority ethnicity groups.

Contextual Factors Analysis

This evaluation includes FDAC sites across multiple Local Authorities. Some FDAC sites will have been operating for over a decade, whilst others will only have launched in 2020. There are also differences in delivery models across sites. This will be explored as part of the Implementation and Process Evaluation (IPE).

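### Read literally, the reunification risk ratio is computed for a typical cluster, not for the population; at the plan's own ICC of 0.70 a population ratio of 1.36 would be reported as about 2.1

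*Supplement*

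**What the plan says.** All references are to protocol version 2.0.

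- **Model** (Analysis plan, Analysis). Reunification is modelled by multilevel logistic regression with intercepts for primary carer, case and site. The doubly robust approach is said to be one that "reduces the risk that the average treatment effect on the treated (ATT) is biased".
- **Definition of the ratio** (Effect Size Estimation). The relative risk ratio is the probability of reunification under FDAC divided by that under non-FDAC, each conditional on covariates X. The random effects do not appear in the definition.
- **Computation of the ratio** (Effect Size Estimation). The plan states: "we will calculate the conditional probabilities from the fitted coefficients of the multilevel logistic regression models by holding the covariates constant at their means". The ratio and its confidence interval then come from nlcom. The handling of the random intercepts is not mentioned.
- **Planning figures** (Minimum detectable effect size calculations). The assumptions include "Clustering of children within parents, with an ICC of 0.70" and a control reunification rate of 25%. From these, "we expect the evaluation will be powered to detect a relative risk ratio of 1.36", stated to equal 9.1 percentage points.
- **RQ6** (Additional Analysis). The placement model has the same three intercepts, and its risk ratio is to be obtained in the same way.
- **Secondary outcomes** (Secondary Analysis). Cessation keeps case and site intercepts. Contested hearing and expert use have a site intercept only. The count of expert types is a Poisson model with a site intercept.

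**The concern.** In a logistic model with a random intercept, the probability at an intercept of zero is not the average probability over clusters, because the inverse logit is not linear. When the outcome is uncommon and the intercept variance is large, the probability at zero lies well below the average, and a ratio of two such probabilities lies further from 1 than the ratio of the averages.

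A ratio built from fitted coefficients and covariate means, with nothing integrated out, is therefore a ratio for a child with average covariates in a typical carer, case and site. The plan does not declare that as its estimand. Its definition, its ATT wording and its planning figures all point to a ratio of average proportions.

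Reunification is the primary outcome, and this ratio is its headline effect size. Readers would naturally set it beside the observed reunification proportions, the 1.36 used for planning, and the proportions in earlier FDAC studies. It would not be on the same scale as any of them. It would also depend directly on an intercept variance that clusters averaging 1.4 children estimate poorly.

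**Working it through.** **1. Reproduce the planning figure.** Inputs from the MDES section: "A type one error rate of 0.05"; "Two tailed significance testing"; power 0.80; ICC 0.70; "No clustering of children within Local Authorities"; R² of 0.20 at level one and 0.10 at level two; 430 cases in total; 1.4 children per case; equal groups (P = 0.5).

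With 406 degrees of freedom (12 Local Authorities, no level-two covariates), M = t(0.975) + t(0.80) = 2.808. Changing the degrees of freedom over about 360 to 430 does not alter the result.

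MDES = 2.808 × √[0.70 × 0.90 / (0.25 × 430) + 0.30 × 0.80 / (0.25 × 430 × 1.4)] = 2.808 × √(0.005860 + 0.001595) = 0.2425

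OR = exp(0.2425 × π/√3) = 1.552

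RRR = 1.552 / (0.75 + 0.25 × 1.552) = 1.364, and 0.25 × 0.364 = 9.1 points.

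This matches the stated 1.36 and 9.1. It puts the level-two R² on the ICC term and uses the exponential for the odds ratio. Appendix F as printed has the R² subscripts the other way round (giving 1.352 and 8.8 points) and a power of e in the odds-ratio line (giving about 0.11). The target is thus 25.0% against 34.1% on the population scale.

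**2. Translate the ICC into an intercept variance.** On the latent logistic scale, variance = ICC/(1 − ICC) × π²/3. At 0.70 this is (0.7/0.3) × 3.290 = 7.68. The plan does not name the scale of its ICC; the latent reading agrees with its own π/√3 conversion.

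**3. Find the linear predictors that give the population rates.** Solve E[expit(η + u)] = p with u ~ N(0, 7.68), by Gauss-Hermite quadrature. For p = 0.25, η = −2.212; for p = 0.341, η = −1.342. The conditional odds ratio is exp(0.870) = 2.39.

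**4. Evaluate at u = 0.** expit(−2.212) = 9.9% and expit(−1.342) = 20.7%. The ratio is 2.10 (2.08 if the population ratio is taken as exactly 1.36).

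**5. Vary the ICC** (population rates 25% and 34.1% throughout).

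| Latent ICC | Variance | Control at u = 0 | FDAC at u = 0 | Ratio at u = 0 |
|---|---|---|---|---|
| 0 | 0 | 25.0% | 34.1% | 1.36 |
| 0.1 | 0.37 | 23.4% | 32.9% | 1.40 |
| 0.3 | 1.41 | 19.9% | 30.1% | 1.51 |
| 0.5 | 3.29 | 15.6% | 26.5% | 1.69 |
| 0.7 | 7.68 | 9.9% | 20.7% | 2.10 |
| 0.8 | 13.16 | 6.2% | 16.1% | 2.61 |

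If 0.70 were instead an ICC on the observed 0/1 scale, the latent variance would be about 28.7 and the ratio about 4.1.

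**6. Isolate the cause.** Integrating over the intercepts returns 1.36. Holding covariates at their means but still integrating gives about 1.38 if covariates carry 10% of the between-parent variance. Nearly all of the gap comes from the random intercepts. In 150 simulated studies from a two-level model (430 families, about 1.4 children each, ICC 0.7), the ratio at u = 0 had median 2.00 (5th to 95th percentile 1.22 to 3.39). The integrated ratio from the same fits had median 1.36 (1.09 to 1.72).

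**7. Other outcomes.**
- Null: a population ratio of 1 gives exactly 1 at u = 0.
- Contested hearing and expert use: with a site intercept only, 1.364 becomes 1.38 at a site ICC of 0.05 and 1.40 at 0.10, for the same illustrative rates.
- Count of expert types: with a log link and a random intercept, the rate ratio is the same conditionally and on average.
- Cessation: no base rate is given. At ICC 0.70, population rates of 70% and 80% (ratio 1.14) give 1.11 at u = 0, nearer to 1.

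**The case against.** **The plan never says that random effects are set to zero.** This is correct. It specifies coefficients, covariate means and nlcom, and is silent on the intercepts. Naming nlcom does not settle the matter, since it only forms the ratio and its standard error. The definition that conditions on X alone could be taken as a sign that averaging was intended. If the analysts do integrate, the discrepancy disappears. What stands is that the computation as written contains no such step and does not match the definition it is meant to implement.

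**A ratio for a typical cluster is a legitimate estimand.** It is, and it leaves the null value where it is, so type I error is not in question. But the plan does not declare it, and it conflicts with the ATT wording and the planning scale.

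**The 0.70 is a planning input, not a fitted variance.** Also correct. A reader might infer that the reported effect will be doubled. The documents support only a conditional statement: the size follows the fitted variance, from no distortion at zero to about 2.1 at 0.70. The simulation omits the three-level structure, the matching weights and the covariates, so it illustrates the mechanism and does not predict the result.

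**The same method serves the secondary outcomes.** A reader might infer that they too are overstated. That does not follow. Two of the three binary outcomes have only a site intercept, the count is unaffected, and for cessation neither the size nor the direction is known.

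**Conclusion.** The point holds for reunification and RQ6, as a mismatch between the stated estimand and the written computation. Read literally, the computation gives a typical-cluster ratio where the plan's definition, ATT target and planning figures call for a population-average one.

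At the plan's ICC of 0.70, a population ratio of 1.36 would appear as about 2.1; at 0.5 as about 1.7; at 0.3 as about 1.5. These reunification figures assume normal random intercepts, an ICC on the latent logistic scale, a control rate of 25%, and no integration by the analysts. For RQ6 the mechanism is the same, but its size has not been computed.

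The matter concerns the size and interpretation of the reported effect, not the validity of the test. It does not establish a material overstatement for the secondary outcomes.

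**What to change.** In Effect Size Estimation, replace the covariates-at-means step for reunification and RQ6 with marginal standardisation:

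1. For each matched FDAC child, predict the outcome with Intervention = 1 and with Intervention = 0, keeping that child's covariates and integrating over the carer, case and site intercepts. For reunification, marginal predictions in margins after melogit do this.
2. Average each set of predictions over the matched FDAC children. They all carry weight 1, so a simple average targets the ATT.
3. Report the ratio of the two averages with its confidence interval.

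Use the same step for cessation, contested hearing and expert use so that all binary outcomes are reported on one scale. The Poisson rate ratio needs no change. A risk difference or a bootstrap interval would be a useful addition but is optional.

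If a typical-cluster ratio is what is wanted, the plan should say so, and should state that it is not comparable with the 25%, 1.36 and 9.1-point figures.

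The cost is one paragraph of wording and a few lines of Stata. No new data are needed.
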